**Table 1. Instruments** 

Variable	Measurement	Timing					
Descriptive (1-2) below							
Maternal, prenatal and perinatal demographics	Age, Race/Ethnicity, parity, BMI, smoking, education, employment, maternal health, delivery mode, antenatal/birth complications, antenatal steroids, type of insurance delivery of more than 1 infant, date and time of birth. (App A; B)	Collected upon entry into study.					
2. Infant demographics	Sex, gestational age, Apgars, weight, head circumference and length.	Collected upon enrollment, end of weeks 1 & 2 and at discharge.					
Time to onset of secretory activation	Hours from delivery to a MOM sodium level of < 20mM (analyzed using an ion selective electrode analyzer, pumped MOM volume of 20 ml in 2 consecutive pumps; maternal report of breast fullness. (App H, App I)	Daily until onset of secretory activation					
Maintenance of secretory activation	Defined as a MOM sodium level < 20 mM analyzed using an ion selective electrode analyzer (HORIBA, Japan). (App H)	Daily for 15 days					
Volume of pumped MOM	Weight of pumped MOM. Total of each vial will be summed for a 24-hour total. (App L)	Daily for 15 days.					
Volume of MOM if infant breastfeeds.	Test weighing - Difference in infant's weight before and after feeding as a measurement of MOM intake. (App L, App N)	Daily for 15 days.					
Milk removal efficiency.	mL of MOM pumped per minute (App M)	Daily on days 8-15 postpartum					
Lactation duration (1-2 below)							
1. Days mothers lactated during infant hospitalization.	Data extracted from electronic medical records and from maternal questioning.	Daily until infant discharge.					
2. Weeks mothers lactated following infant discharge from the NICU.	Monthly maternal text message with hyperlinked surveys through Qualtrics. (App. J)	Monthly until lactation cessation or infant is 6 months of age.					
Maternal perceptions of comfort, effectiveness, efficiency, and convenience	Hyperlinked surveys through Qualtrics (App K)	Complete Part A only (Day 6-8) Complete Part A & B (Day 9-12) if randomized to new pattern					
Infant MOM consumption (1-3 below)							
1. Proportion of feeds consisting of MOM.	Data extracted from medical record or via test weighing of infants if they breastfeed. (App N)	Daily for 15 days					
2. Proportion of feeds consisting of MOM at discharge	Data extracted from medical record or via test weighing of infants if they breastfeed. (App O)	For 24 hours prior to discharge					
3. Duration of partial or exclusive MOM feedings after discharge	Monthly maternal text message with hyperlinked surveys through Qualtrics. (App J)	Monthly until lactation cessation or infant is 6 months of age.					
Length of NICU hospital stay; infant nutritional, and health outcomes	Days infant remained hospitalized in the NICU, nutritional and health outcomes	From birth until discharge.					
Covariates (1-6) below							
1. Demographic data	Maternal: Race/Ethnicity, delivery of > one infant, delivery mode, parity, BMI, co-morbidities. Infant : Gestational age at birth, birthweight, Apgar score. % of type of feeding consumed (MOM, donor human milk, formula). (App A, App N)	Upon entry into study and during the 15-day study period					
2. Number of pumping sessions per day	# of times a mother pumps her breasts per day. (App L)	Daily for 15 days					
3. Skin-to-skin care	Total minutes and episodes of skin-to-skin care.	Daily for 15 days.					

4. Maternal mood	Results of 2 MAACL-R tests completed by mom.	Prior to her hospital discharge and at 15					
	(App D)	days postpartum.					
5. Lactation experience	(a) Feeding plan prior to delivery, previous experience	Before maternal hospital discharge (a)					
	with breastfeeding and/or pumping, lactation intent, home	At end of study (b)					
	pump status (b) Lactation intent, lactation goals lactation						
	consultations, galactagogues, mastitis diagnosis and						
	treatment, use of hormonal birth control, home pump status						
	(App C)						

Table 2: Timeline of events over the 15-day study

Measure	0*	1	2	3	4	5	6	7	8	9	10	11	12	13	14	15
Consent, maternal interview		Х-	-X													
Pumping optimization		X-		-X			X-		-X							
MOM NA/K Level		Х-														- X
Lactation risk assessment							X-		-X							
Randomization							X-		-X							
Determination of CTV																X
Measures of pumped milk volume		X	X	X	X	X	X	X	X	X	X	X	X	X	X	X
Measures of infant consumption of MOM		X	X	X	X	X	X	X	X	X	X	X	X	X	X	X
Maternal perception survey (Part A)							Х-		-X							
Maternal perception survey (Part A/B)										Х-		-X				
MACCL			Х-	-X												X
Lactation experiences			X													X

\* = day of birth

## 7. Possible Discomforts and Risks:

It is possible that mothers may find the alternate breast pump patterns uncomfortable. Should this happen, they will be asked if they would like to be withdrawn from the study and use their own breast pump consistent with standard care for all mothers pumping MOM for their infants in the NICU use.

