**BPSPs 1** and 2. The current study posits that two alternative BPSPs may be more effective in increasing pumped milk volume and thus achievement of CTV in breast pump-dependent mothers by offering alternatives to the "one size fits all" approach of using the standard care Symphony Plus BPSP after achievement of SA. Eligible mothers will have demonstrated faltering lactation (<350 mLs/day pumped MOM on postpartum day 6-8) after achievement of SA. Both BPSP 1 (slower rate with a long hold time and higher starting vacuum pressure) and BPSP 2 (faster rate with longer hold time during peak vacuum pressures) have been trialed in mothers of preterm infants, but not during this early postpartum time period nor with mothers who experience faltering lactation. Although different in the manner in which suction is applied and maintained during each pump cycle, both BPSPs have greater area under the suction curve (accomplished via modifications in suction pressure and duration) than does the standard Symphony Plus BPSP. Theoretically, these BPSPs afford "more time" per cycle for MOM removal, and may optimize endocrine and autocrine regulation of lactation, increasing MOM synthesis. These outcomes are reflected in the specific aims. An additional interest is whether these alternative BPSPs may be especially effective and/or efficient in mothers with co-morbidities such as overweight and obesity, for whom the extra area under the suction curve may improve MOM removal. However, equally important is maternal perceptions of comfort and ease of use for both BPSPs, especially during the early postpartum period when the mammary tissues are more prone to discomfort with either breastfeeding or breast pump use.

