The NICU at UF Shands admits infants that are racially diverse regardless of private or Medicaid insurance coverage. All mom that meets the above criteria would be eligible for enrollment. Informed consent will be obtained by mothers in their postpartum hospital room or in the NICU while visiting their infant prior to 48 hours postpartum. The informed consent includes mother's permission to access their infant's chart to collect information up until infant's discharge. The infant has no study interventions. In the rare instance that an infant breastfeeds, intake will be determined through test weighting (infant weight pre and post breastfeeding). Prior to the mother's hospital discharge, she will be provided an empty payment card where participants will receive compensation, by adding payments for completing study events, listed below. After enrollment, a 2-minute maternal interview will be used to collect information to determine pre-pregnancy BMI and other factors that might impact lactation success (Appendix B). Information will be collected related to pumping frequency and pumped milk volume prior to enrollment (Appendix I). All enrolled mothers will be provided breast pumping instructions to optimize their pumping behaviors prior to achievement of secretory activation. This 30-minute optimization session will be provided by a Research Nurse Coordinators, who is also an International Board-Certified Lactation Consultant (IBCLC). The instructions will be standardized using a score card, which provides prompts for education discussion and video links about pumping practices, breast and nipple assessment, breast shield sizing and comfort. (Appendix F). A daily sample of 0.3 mL of pumped MOM (if mother has pumped at least 5mL/day) will be tested for MOM sodium level as an indicator of secretory activation. At day 6-8 postpartum, mothers at high risk of suboptimal lactation will be identified and randomized to one of three BPSPs Mothers will be determined to be at risk if they have (1) achieved secretory activation (change from small volumes of colostrum to large volumes of more mature milk; determined by a milk sodium level < 20 mM) and (2) have a pumped milk volume < 350 mL/d. Mothers who are identified as being not at risk for suboptimal lactation (have achieved secretory activation and their pumped milk volume is > 350mL/d) will not be randomized but will continue with standard care regarding BPSPs, and continue to have data regarding lactation collected. Mothers who do not reach SA, determined by a milk sodium level > 20 mM, will be withdrawn from the study and referred to the UF Shands Lactation Team. All mothers that achieve SA, will be provided a second 30-minute standardized breast pumping optimization session with instructions by a Research Nurse Coordinator who is an IBCLCs at day 6-8 postpartum. Mothers will complete the Maternal Perceptions Survey (Appendix K/Part A only) before starting new pattern. If randomized, Moms will complete the Maternal Perception Survey (Part A/B) on Day 9-11. A score card, designed for mothers who have already achieved secretory activation, includes educational prompts and video links regarding milk volume, pumping behaviors, breast and nipple assessment, flange fit and comfort will be utilized. (Appendix G). Should a mother be unable to obtain transportation to the NICU, they will be provided transportation through Uber Health, provided they live within a 60-mile radius of UF Shands due to cost limitation of study.

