- (2) All mothers will be provided pre-weighed and labeled vials to place their MOM following each expression per NICU policy and asked to bring all expressed MOM to the NICU. It is standard care in this NICU that all MOM brought to the NICU is weighed and the volume recorded in the infant's EMR (all mothers). Volume of pumped MOM will be determined by weight (1 mL = 1 gram). All MOM will be weighed by human milk technicians who have worked in this NICU's designated Human Milk Room since 2013, are not involved with direct care of either mother or infant and will be blinded to the group assignments. There are currently 7 human milk technicians covering the Human Milk Room 24/7 who

weigh and log each container of MOM delivered to the NICU. After MOM is weighed, it is available for infant consumption. Measurement of MOM volume (through weighing) will occur daily for 15 days. Although highly unlikely due to immaturity, if an infant breastfeeds, test weighing will be used to calculate volume of MOM consumed. Test weighing or weighing infants prior to and following breastfeeding, is an accurate method of determining intake during breastfeeding. Prior to each breastfeeding session, infants will be weighed. Weight will include clothing, diaper, and blankets worn by the infant. Following breastfeeding, the infant will be weighed again, clad in the same clothing on a Baby Weigh scale (Medela, Inc., McHenry, Ill) to the nearest 0.2g. Differences between pre- and post-feeding weights will be recorded in the infant's EMR and added to the total volume the mother expressed on that day.

**Aim 2:** A second aim will compare lactation outcomes including 1) maintenance of secretory activation, 2) rate of increase in daily pumped MOM volume, 3) whether or not mothers reach coming to volume (CTV; pumped milk volume of  $\geq 500$  mL by day 14 postpartum). daily pumped MOM volume, 4) cumulative MOM volume over days 1-7 and 8-15) milk removal efficiency, and 5) lactation duration.

**Maintenance of secretory activation**. For all mothers enrolled in the study, maintenance of secretory activation will be defined as a daily MOM sodium level < 20mM. A research assistant, blinded to group assignment, will collect 0.3 mL of MOM daily from

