vials of MOM brought to the NICU and place the sample onto the sensor of an ion selective electrode analyzer (HORIBA, Japan) which is a hand-held machine used for sodium and potassium analysis (see photo), has been validated for accurate analysis of human milk sodium and potassium levels, and will be calibrated prior to every analysis. Although both sodium and potassium are secreted into milk via transcellular pathways, sodium but not potassium is also transferred from the maternal circulation via patent paracellular pathways. Thus, it has been suggested that a milk sodium to potassium ratio would standardize sodium level for individual women. While no differences have been reported between the ability of sodium alone versus a Na:K ratio to predict pumped milk volume, we will also measure potassium levels. (Appendix H) To ensure accuracy, individuals performing sodium analysis will be trained and evaluated prior to beginning analysis and quarterly. Our team is highly skilled in milk collection, processing and analysis.

Rate of increase in daily pumped MOM volume, achievement of secretory activation (Yes/No), and cumulative MOM volume over days 1-7 and 8-15 postpartum. MOM volume will be measured as discussed in Aim 1 and each of the outcomes determined.

Milk removal efficiency. Efficiency of milk removal will be determined by mls of MOM pumped per minute of pumping (cumulative per day and cumulative over days 8-15). Minutes of pumping is measured and recorded on the SMART pump (Appendix M).

Lactation Duration. Number of days a mother lactates (either via breastfeeding or expressing MOM) during her infant's hospitalization and whether or not she is lactating at infant discharge will be collected. Mothers will be determined to have ceased lactation when they are no longer bringing MOM to the NICU, are not placing the infant to breast for nutritive or non-nutritive sucking, and states they are no longer lactating when questioned. If still lactating at their infant's NICU discharge, mothers in all groups will be questioned regarding their continued lactation through monthly text message hyperlinked surveys via the Qualtrics platform until their infant is 6 months of age or she has ceased lactation. If a mother ceased lactation within the past month, she will be asked the week within the past month she discontinued lactating (Appendix J).

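### Section 7 offers a mother with discomfort only withdrawal from the study, with no option to stop the pattern and stay in follow-up, which risks treatment-related missing data

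*Protocol*

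**What the plan says.** Section 7 of the protocol (Possible Discomforts and Risks) states "It is possible that mothers may find the alternate breast pump patterns uncomfortable" and continues "Should this happen, they will be asked if they would like to be withdrawn from the study and use their own breast pump". It adds that this is in line with standard care for mothers pumping for a NICU infant. This is the only instruction in the visible text for a randomised mother who does not tolerate her pattern.

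The one other withdrawal rule (Sample and Setting, and the compensation list after it) covers mothers who do not reach secretory activation. It applies before randomisation and ends their participation.

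Follow-up on standard care without an assigned pattern is described for one group only, the mothers not at risk, who "will not be randomized but will continue with standard care regarding BPSPs, and continue to have data regarding lactation collected".

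Several measurements do not need the study's SMART pump:

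- **Volume.** Under Aim 1, milk brought to the NICU is weighed and entered in the infant's record for every mother, as standard care.
- **Sodium.** Under Aim 2, it is sampled from milk brought to the NICU.
- **Later lactation.** Also under Aim 2, "mothers in all groups will be questioned regarding their continued lactation through monthly text message hyperlinked surveys".
- **Chart access.** Consent gives "permission to access their infant's chart to collect information up until infant's discharge" (Sample and Setting).

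**The concern.** The rule ties a treatment decision (stop this pattern) to a data decision (leave the trial). A mother in discomfort can continue the pattern or be withdrawn. The middle course, stopping and being followed, is not offered.

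Four features of this trial make that matter:

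- **The trigger is treatment-related.** Section 7 names discomfort for the alternate patterns. Section 4 (Background) says both have a larger area under the suction curve than the standard pattern, and that comfort is important "especially during the early postpartum period when the mammary tissues are more prone to discomfort with either breastfeeding or breast pump use".
- **The timing is unfavourable.** The pattern is used for 7 days from day 6-8 and the primary outcome is volume on days 8-15, so exits fall in or just before the primary window.
- **Comfort is itself an outcome (Aim 3).** Mothers who leave because of discomfort are those whose ratings matter most.
- **There is no visible reserve.** The plan randomises 90 mothers, 30 per arm, and the power statement uses all 30.

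An SAP can choose an estimand and a missing-data method. It cannot supply volumes, sodium values or ratings that were never collected.

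**Working it through.** **1. Does any text separate stopping from leaving?**

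| Place | Who | What it provides |
|---|---|---|
| Section 7 | Randomised mother with discomfort | Asked whether she wants to withdraw and use her own pump |
| Sample and Setting | Mother not reaching secretory activation | Withdrawn before randomisation |
| Sample and Setting | Mother not at risk | Not randomised, standard care, data continue |

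No row covers a randomised mother who stops the pattern and stays. The protocol also does not say whether chart data stop when a mother withdraws under section 7.

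**2. Reproduce the plan's power.** Inputs from Sample Size Determination: two-sided alpha 0.02, two-sample t-test, 30 per group, difference 300 mL, SD 350, stated effect size 0.84. Since 300/350 = 0.857, both values are carried.

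With arm sizes n1 and n2, the noncentrality is d / √(1/n1 + 1/n2), on n1 + n2 − 2 degrees of freedom. Power is the probability that |t| exceeds the critical value.

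For 30 v 30 and d = 0.84: √(1/30 + 1/30) = 0.2582, noncentrality 0.84/0.2582 = 3.253, critical value 2.392 on 58 df, power 80.25%. The stated 80% is reproduced. With d = 0.857, power is 82.0%.

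**3. Bound the loss.** The protocol gives no withdrawal rate, so the rates below are assumptions. Standard care is held at 30, and each leaver from the alternate arm is counted as giving no primary data.

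| Assumed loss in alternate arm | Arms | Power, d = 0.84 | Power, d = 0.857 |
|---|---|---|---|
| None, or hospital record captures every leaver | 30 v 30 | 80.2% | 82.0% |
| One mother | 30 v 29 | 79.5% | 81.2% |
| 10% | 30 v 27 | 77.7% | 79.5% |
| 20% | 30 v 24 | 74.6% | 76.5% |
| 30% | 30 v 21 | 70.7% | 72.7% |

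Volume is recorded daily, so a mother who leaves mid-window has already given some days. For any given loss rate, the true position lies between the first row and the row for that rate.

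**4. Bias.** In a completers-only mean, the shift equals the fraction lost times the difference between the stayers' and leavers' means. The protocol supports a value for neither, so no bias figure is given, and its direction is open.

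**5. Comfort ratings.** Which leavers would lack an on-pattern rating depends on which survey timing governs. Sample and Setting and Table 2 give day 9-11, Table 1 gives day 9-12, and the Aim 3 procedures give within 7 days of study completion. Under the earlier timings, those who leave in the first days are lost. Under the last, anyone who leaves may be.

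**The case against.** The strongest reply is that the harm depends on something the protocol does not state. Section 7 is a short risk statement that makes an offer; it does not set a stopping rule. It neither requires a mother to leave nor says that data collection ends. Chart permission runs to infant discharge, milk brought to the NICU is weighed as standard care, and a mother using her own pump would probably still bring milk. The primary outcome could therefore survive largely intact. Consent pages are not among the text reviewed and may say what happens to data after withdrawal. Mothers are blinded to pattern, and the Background links early discomfort to any pump use, so uneven loss between arms is conjecture. The loss rates are assumed, and at low loss the power cost is small.

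Much of this stands, as limits on size. Withdrawal is optional, uneven loss is not shown, and the no-loss case is a legitimate bound. It does not remove the point. Elsewhere in this protocol, being withdrawn ends participation. Chart permission does not by itself cover surveys or research sampling of milk. Blinding does not stop a mother feeling discomfort. If the intention is to keep following these mothers, section 7 should say so, because site staff will act on what it says.

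**Conclusion.** The concern holds as a design choice that should be considered for change. Section 7, the only visible conduct rule for this situation, joins stopping the pattern to leaving the study. Followed as written, it can lose day 8-15 volume, sodium and comfort data for a reason related to treatment.

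The size is uncertain. The power cost against standard care runs from nothing, if record-based volume continues for every leaver, to about 9 percentage points (80.2 − 70.7 = 9.5 at d = 0.84; 82.0 − 72.7 = 9.3 at d = 0.857) if an assumed 30% of an alternate arm leaves without contributing primary data. At the stated effect size of 0.84, one mother lost in this way takes power just under 80%. Informative loss matters more than power, but its size and direction cannot be derived from the document. Confidence is medium, because the protocol is silent on data collection after withdrawal.

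**What to change.** Reword section 7, for all three arms, so that a mother may stop the assigned pattern without leaving the study. With her agreement, continue NICU-weighed volume from the infant's record, milk sodium, infant feeding data and the surveys. Give the Part A/B perception survey at the time of stopping if it has not been completed. Record discomfort-related stopping by arm. State that full withdrawal remains her right at any time.

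The cost is one or two sentences, since follow-up without the SMART pump already runs for the non-randomised mothers. There are three downsides. Record-based volume may miss milk that is not brought to the NICU. Efficiency in mL per minute is not measured once the SMART pump is given up. Volume after stopping reflects a treatment-policy comparison and no longer the effect of continued use of the pattern.

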## 8. Possible Benefits:

There is no direct benefit to mothers completing this study. Moms may possibly benefit from having a hospital grade breast pump to use at home for the 2-week study. Mothers who use alternate breast pump patterns may have improved lactation outcomes and their infants could receive higher doses of MOM.

## 9. Conflict of Interest:

There are no conflicts of interest.

